All documents that include identifying information (i.e. names, addresses and telephone numbers) will immediately be separated from the patient assessments, training materials, and

recordings. These items will be stored by research staff authorized by the PI in a locked file and an identifying case number will be generated. The PI and authorized research staff will be the only persons with access to the locked filing cabinet and/or any information or files that link the case number with any patient identifying information. No reports will be made public using any names or identifying information. Raw data and accompanying research protocols will be kept for at least 7 years post publication of findings. Strict measures to assure confidentiality of the data will be taken. Computerized data will be identified by participant number only. All computerized data is stored on a secured central server in the MGH Data Center and backed up daily. The MGH research team, as part of a hospital network is HIPAA compliant and adheres to strict data safety guidelines, implementing network firewalls, antivirus systems, internet screening and auditing systems and network intrusion detection systems. All research staff PCs are password-protected and have standardized, full featured, software and hardware configurations. Only research staff authorized by the PI will have access to the data. The lead analyst working with the data is the only person on-site with network level administrative password privileges. Offsite, only authorized MGH IT department technicians can access the server holding this data. The original data and the encrypted data will not be transported or used at any other location and the data will not be copied onto other computers, discs, CDs etc. We will maintain all print-outs, electronic files, personal computers with restricted data on the hard drives, or other physical products containing data in locked cabinets, file drawers or other secure locations when not in use. Printed material that includes analyses based on restricted data will be promptly destroyed. At the end of the project, all files that include restricted data will be destroyed, including copies and subsets on the MGH server or any project computers. We plan to share and analyze data between the Disparities Research Unit site in Boston and the University of North Carolina site in Greensboro. PIs, Project Managers, and community site partners will work closely to ensure data is protected across sites.

Given that the CAT-MH screening tool and our Strong Minds-Strong Communities Intervention (delivered by CHWs) are relatively new, we will make extensive efforts to ensure the safety of study participants, and to systematically track risks, issues, and outcomes across the MA and NC sites. We will create a monitoring registry where we can tabulate and track any human subjects and systematic issues that arise with implementation across sites, and between intervention and control conditions. We will identify a core set of participant issues that will be flagged if they occur: 1) cases with no improvement or an increase in symptom scores on key outcome variables; 2) no-show for scheduled appointments; 3) staff concerns about participant's well-being; or 4) site operational issues (such as space limitations for sessions, transportation challenges, resistance by site staff to any aspect of the study, such as the procedures for the emergency protocol etc.). These four areas will be programmed into the registry, with an area for notes and additional details. The registry will be maintained by the Project Manager in conjunction with the Care Manager at each site, who will set up the registry to track participants by case ID, clinical site, and date of occurrence. We will create logons for CHWs and Research Assistant interviewers at each site, who can enter information pertaining to their cases. We will set up specialized permissions at the user level to ensure that Research Assistants remain blinded to any information about participant condition. The Project Manager and Care Manager will review the data in preparation for weekly team and supervisor meetings and will download the registry data to review with study staff and supervisors. At the onset of the project, we will work with the study data analysts to program an algorithm to easily query the system to display cases with elevated issues in each of the 4 categories. This process will allow us to flag and highlight individual cases but also generate reports on the frequency of any given issue within and across the sites. Solutions will be discussed and determined by the research team including the PIs at each site, and these will be reintegrated into the protocol by the Project Managers. We will thus systemize our monitoring of outcomes and challenges to view patterns and

optimally address them. The registry will also inform our understanding of implementation challenges overall.

To improve the security of data collection, we will be working with the Dimagi Corporation, using their secure server to collect data via the CommCare HQ technology. This is installed in a series of secure tablets through which research assessments will be collected. Dimagi is a HIPAA compliant, secure, encrypted server that allows for host intrusion and intrusion monitoring system. All technology can only be accessed through secure and password servers. The CommCareHQ application will be installed on tablets and these tablets will be made available to research assistants serving as interviewers on the PCORI study. Our research assistants have already undergone training by Dimagi.

The Dimagi CommCare HQ system is a healthcare data collection application installed on tablets designated solely for study use. Dimagi is bound by a confidentiality agreement and has various data safeguards in place including: a secure, multi-tenant system hosted in Dimagi's Secure Private Cloud, based in Chicago, IL; Network Intrusion Detection System (NIDS); Web Application Firewall (WAF); Host Intrusion Detection System (HIDS); Server Event and Information Management (SEIM); encrypted hard drives; data destruction policy; and being Health Insurance Portability and Accountability Act (HIPAA) compliant.

All audio-recorded interviews will also be uploaded immediately to the same secure, password protected server maintained at MGH. No reports will be made public using any names or identifying information. Our coded dataset will be stored on a secure central server. Only authorized research staff approved by the site Institutional Review Boards will have access to the data. PHI will be destroyed according to standard protocols, 7 years after the completion of the study.

C. Outcomes monitoring

NA

XI. Adverse event reporting guidelines:

A. Sample Self-Harm/Risk Emergency Protocol

The following protocol is an example of the mental health self-harm/risk reported to study staff for patient participants in the intervention. We would adapt this protocol to study sites per local requirements and for physical health issues that might be experienced.

The emergency procedure is prompted if a patient endorses a 4 or 5 on the Paykel suicidality screener over the last 30 days. The questions include: “Has there been a time in the last 30 days/since the last assessment when you reached the point where you seriously considered taking your own life, or perhaps made plans how you should go about doing it?” = yes or “Has there been a time in the past 30 days/since the last interview when you made an attempt on your own life?” = yes.

- 1) At the end of the session or interview, study staff should inform the participant: *“I am not a clinician; however, when anyone tells us they’ve been feeling this way recently, we connect them with a clinician who can ask some questions about how you’ve been feeling. We will also contact your primary care doctor to let them know about this conversation and make sure you are safe. We want to ensure your safety, so let me connect you right now. Could you please tell me where you are located right now?”*

2) **Study staff should immediately connect the patient to the correct Emergency Services provider** for assessment.

- Place the patient on hold (or have them wait a moment when in person).
- When speaking to emergency services team, refer to the study: I have a patient on the line as part of the research study who scored high on a suicide screening tool. I am not a clinician, and am hoping the patient can be assessed for risk by phone -- he/she has given consent to this as part of the study.
- Take the name of the person who you are talking to.
- The emergency services provider will need the following information from you:
 - patient's name
 - phone number
 - present location
 - what was said by patient re: suicidality
- If a Spanish, Mandarin, or Cantonese speaking clinician is not readily available, study staff are allowed to translate only in the capacity of informing the patient of what the emergency services provider says are the 'next steps' (i.e., someone is going to call you back in 5 minutes, etc.)

If for some reason, the participant is not able to be or refuses to be connected right away you should:

- 1) Provide the patient with the emergency services contact number, depending on where they are located.

2) Contact the emergency services provider based on where the patient is located and share the pertinent information as described above. Immediately inform the study PI and your supervisor.

Emergency Protocol Documentation Form

Patient ID #: _____

Date: _____

Items endorsed:

4 on the past 30 days Paykel

5 on the past 30 days Paykel

Description of event: _____

Primary Care Provider's name: _____

Information to collect for Emergency Services

Name _____

Contact phone number right now _____

Where the patient is right now _____

What the patient said about suicidality _____

Patient Date of Birth (if available) _____

Patient Insurance (if available) _____

Name of person who you talked to _____

Post-call checklist

Send Message to PCP _____

Email to Site Leader and PI _____

Inform PCP of outcome _____

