The purpose of this research project is to reduce mental health disparities for racial/ethnic and linguistic minorities by establishing community-ACO-academic partnerships to collaborate in building capacity for mental health care; training Community Health Workers (CHWs) to provide an integrated, evidence-based intervention in community settings linked to ACOs; and addressing participants' activation and social needs through a care manager that connects participants to needed services. We propose a model that includes CHWs as mental health providers, who offer an evidence-based mental health intervention called Strong Minds-Strong Communities to address the shortage of trained providers who can offer culturally congruent mental health service in non-English languages in Medicaid-based ACOs, thereby expanding ACO infrastructure and increasing access to and quality of mental healthcare for racial/ethnic and linguistic minorities in North Carolina (NC) and Massachusetts (MA).

The following protocol focuses on Aim 2, the clinical trial portion of the study.

III. Study Design Summary

A. Inclusion/Exclusion Criteria

Inclusion Criteria: Latino, Asian, Black (African American or Afro-Caribbean), or non-Latino White adults 18+ years of age with moderate to severe symptoms of depression and anxiety. This includes participants who score 50+ on the CAT-MH depression administered in English/42+ for the CAT-MH depression administered in Spanish or Chinese and/or 51+ for the

CAT-MH anxiety administered in English /41+ for the CAT-MH administered in Spanish or Chinese; and/or a positive score on the CAT-MH Major Depressive Disorder, and without any mental health care (therapy sessions with psychiatrist, psychologist or social worker) in the past 3 months or upcoming in the next month. Participants must speak English, Spanish, Mandarin, or Cantonese.

Exclusion Criteria: Participants will be excluded if there is evidence of: (1) history of psychosis, mania, or psychotic symptoms; (2) specialty mental health treatment within past 3 months; (3) upcoming behavioral health appointment (pharmacological not excluded); (4) evidence that the participant lacks capacity to consent (measured by a validated screener); (5) evidence of current suicidal risk or harm to others (affirmative responses on Paykel suicide questionnaire); and (6) severe alcohol or substance dependence (CAT score 70+, showing a high level of risk in substance use).

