Moderators. In Goal 2, race and ethnicity will be used as a moderator of the main independent variable (intervention condition). Using self-reported information, participants will be classified into four mutually exclusive categories: Latinx, non-Latinx Black, Asian, and non-Latinx White. In Goal 3, language will be used as a moderator of the main independent variable (intervention condition). Using self-reported information, participants will be classified into four mutually exclusive categories: English, Spanish, Mandarin, and Cantonese. In Goal 4, the site of recruitment will be used as a moderator of the intervention condition. Participants will be classified into two mutually exclusive categories of place of residence: North Carolina or Massachusetts.

Endpoints. The primary endpoints will be change from baseline in depression and anxiety symptoms, level of functioning, and perceived quality of care at month 6 (end of intervention) and at month 12 (6-months post-intervention). The key secondary effectiveness endpoints will

be the change from baseline in the score on the CAT-MH depression (range 0 to 100 with higher scores indicating worse depression symptoms) and the CAT-MH anxiety (range 0 to 100 with higher scores indicating worse anxiety symptoms) at month 6 and 12. The primary and key secondary effectiveness endpoints will be also evaluated in prespecified subgroup analyses based on participant's race and ethnicity, language, and site. Other exploratory endpoints will include changes from baseline in HSCL-25, WHODAS 2·0, PoC-OP, CAT-MH depression, and CAT-MH anxiety scores at month 3, about midway through the intervention. Finally, the primary and key secondary effectiveness endpoints will be evaluated in exploratory subgroup analyses based on the participant's baseline severity of depression and anxiety.

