Statistical Analyses. A two-sided P value of 0·05 will be used to calibrate the significance and false discovery rate. For the primary and key secondary endpoints, we will employ a Benjamini-Hochberg step-down procedure to adjust for the multiple comparisons across 5 outcome scores (HSCL-25, WHODAS 2·0, PoC-OP, CAT-MH depression, and CAT-MH anxiety) at 2 follow-up points (months 6 and 12). If the lowest of the ten P values was less than 0·005 (0·05 ÷ 10), it will be considered to be significant; the second lowest P value will be considered to be significant if less than 0·0056 (0·05 ÷ 9); the third lowest P value will be significant if less than 0·006 (0·05 ÷ 8); and so on. Primary and key secondary efficacy endpoints will be separately analyzed using a general linear model to estimate the treatment effect. Except for PoC-OP, baseline outcome scores will be included as covariates in all analyses. Site (Massachusetts versus North Carolina) will also be included as covariate in all analyses. This general linear model has the following form:

$$y_{i,post-baseline} = \alpha_0 + \alpha_1 Intervention_i + \alpha_2 y_{i,baseline} + \alpha_3 site_i + \varepsilon_i$$

where $y_{i,post-baseline}$ represents an outcome measure for participant i at either 6- or 12-months post-baseline. $Intervention_i$ will be an effect-coded variable equal to -0.5 if participant i was randomized to the control group and equal to 0.5 if participant i was randomized to the intervention group. $y_{i,baseline}$ is the baseline measure of the outcome (except for PoC-OP), $site_i$ is a binary indicator equal to one if participant i was recruited in Massachusetts and equal to 0 if recruited in North Carolina, and ε_i is an error term. Because participants will be recruited in multiple CBOs/clinics across the two sites, in sensitivity analyses we will use generalized linear mixed models with a random intercept accounting for clustering within CBOs/clinics for each primary and key secondary effectiveness endpoint.

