We will conduct analysis of missing data at either endpoint (primary or exploratory) to test whether that, conditional on the observed baseline variables (including baseline outcome scores), the missing at random assumption is plausible. Missing data for all statistical models (primary and key secondary endpoints, exploratory endpoint, prespecified subgroup analyses and exploratory subgroups analyses) will be handled using model-based imputation. For example, missing values to analyze change from baseline in HSCL-25 scores at the 6-month endpoint will be imputed using a general linear model where HSCL-25 scores at month 6 will be the dependent variable. An effect coded variable for intervention condition, HSCL-25 scores at baseline, and a binary indicator for site (Massachusetts versus North Carolina) will be included as predictors. The model further will also include the auxiliary baseline variables associated with missingness (e.g., participant's age or gender). The same model-based imputation will be employed for all primary and key secondary endpoints, and the exploratory endpoint. Imputation models for subgroup analyses (prespecified and exploratory) will add the moderator and its interaction with intervention condition as predictors. For each model, 20 imputed datasets will be generated. Analyses of imputed data will use Rubin's rules to obtain pooled estimates and their standard errors.

C. Power Analysis (e.g., sample size, evaluable subjects, etc.)

The proposed study aimed to recruit 1,200 participants equally distributed across sites (North Carolina and Massachusetts) and intervention conditions (Intervention and Control). That is $N = 600$ intervention participants (300 in North Carolina and 300 in Massachusetts) and $N = 600$ enhanced usual care participants (300 in North Carolina and 300 in Massachusetts).

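### CAT-MH entry cut-offs differ by language, but the main CAT-MH models have no language term: no bias, and a small precision gain available at almost no cost

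*Combined protocol and SAP*

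**What the plan says.** **Eligibility (III.A, Inclusion/Exclusion Criteria).** For depression, a participant qualifies who "score 50+ on the CAT-MH depression administered in English/42+ for the CAT-MH depression administered in Spanish or Chinese". For anxiety, the English cut-off is 51+, followed by "CAT-MH anxiety administered in English /41+ for the CAT-MH administered in Spanish or Chinese". These routes are joined by and/or, and a positive CAT-MH Major Depressive Disorder result is a further route.

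**Endpoints (VII.A, Endpoints).** Change in CAT-MH depression and in CAT-MH anxiety, each on a 0 to 100 scale, at months 6 and 12 are the key secondary endpoints. They supply four of the ten tests in the multiplicity procedure.

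**Main model (VII.A, Statistical Analyses).** The model contains arm, baseline score and site: "Except for PoC-OP, baseline outcome scores will be included as covariates in all analyses", and "Site (Massachusetts versus North Carolina) will also be included as covariate in all analyses". Language is not in it. Language enters only as the Goal 3 moderator, in the prespecified subgroup analyses.

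**Imputation (VII.B, Missing data).** The worked example names these predictors: "An effect coded variable for intervention condition, HSCL-25 scores at baseline, and a binary indicator for site". It then adds "auxiliary baseline variables associated with missingness", with age and gender as examples. The same approach applies to the other endpoints. Imputation for the subgroup analyses also includes the moderator and its interaction with arm.

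**The concern.** The eligibility rule treats a Spanish or Chinese score of 42 as the counterpart of an English score of 50 for depression, and 41 as the counterpart of 51 for anxiety. The main model then fits one regression of follow-up on baseline across all languages.

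If the offset is present at both visits, a single pooled slope below 1 cannot remove all of it. Two participants of equal severity but different language would have different predicted and observed follow-up scores, and the unexplained part of that difference goes into the error term.

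What is at stake is the width of the confidence intervals and the power of the four CAT-MH tests. HSCL-25, WHODAS 2.0 and PoC-OP are not touched by the CAT-MH cut-offs.

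**Working it through.** **Inputs from the documents**
- Cut-off gaps, D (III.A): 50 − 42 = 8 (depression) and 51 − 41 = 10 (anxiety).
- Effective sample (VII.C): 1,200 × 0.87 = 1,044, or 522 per arm; effect size 0.20; two-sided 0.05; stated power 87%.

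**Inputs assumed, because the documents do not give them**
- Within-language SD of CAT-MH, s: 12 to 20.
- Within-language baseline to follow-up correlation, r: 0.3 to 0.7.
- Share assessed in Spanish or Chinese, p: 0.5 to 0.7. Section VII.C gives race and ethnicity (63% Latinx, 13% Asian), not language.
- The cut-off gap applies as a constant offset D at baseline and follow-up.

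**1. The plan's own power figure.** Φ(0.20 × √(522/2) − 1.960) = Φ(3.231 − 1.960) = Φ(1.271) = 89.8%, against the stated 87%. The stated figure does not reproduce from its stated inputs, but it is on the cautious side and nothing below depends on it. Both starting points are carried forward.

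**2. Residual variance with and without language.** Let b = p(1 − p)D², the between-language variance.
- Without language: V0 = (s² + b) − (r s² + b)² / (s² + b).
- With language: V1 = s²(1 − r²).
- Share of remaining variance explained by language: 1 − V1/V0.
- Participants' worth: 1,044 × (1 − V1/V0).

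V0 uses the pooled slope, (r s² + b)/(s² + b). It is steeper than r because baseline itself carries the offset. Using the within-language slope instead would overstate the loss. Site is left out of these formulas; if the language mix differs by site, the site term would absorb a little more.

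**3. Worked case: D = 10, s = 15, r = 0.5, p = 0.5.**
- b = 0.25 × 100 = 25; s² + b = 250; r s² + b = 137.5; pooled slope 0.55.
- V0 = 250 − 137.5²/250 = 174.375; V1 = 225 × 0.75 = 168.75.
- V0/V1 = 1.033; share 3.2%; worth 1,044 × 0.0323 = 34 participants.
- With no baseline adjustment the ratio would be 250/225 = 1.111, so baseline already removes most of the excess.

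**4. Range over the assumed grid**

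| Case | D | s | r | p | V0/V1 | Share | Participants |
|---|---|---|---|---|---|---|---|
| Smallest | 8 | 20 | 0.7 | 0.7 | 1.006 | 0.6% | 6 |
| Middle, depression | 8 | 15 | 0.5 | 0.5 | 1.022 | 2.2% | 23 |
| Middle, anxiety | 10 | 15 | 0.5 | 0.5 | 1.033 | 3.2% | 34 |
| Largest | 10 | 12 | 0.3 | 0.5 | 1.080 | 7.4% | 77 |

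**5. Power for one test at 0.05, before multiplicity adjustment.** In the worked case, Φ(3.231 × √1.033 − 1.960) = 90.7%, up from 89.8%. Starting from the stated 87%, it becomes about 88%.

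**6. Bias.** Simulated trials of 1,044 participants (1,500 runs per scenario; SD 10 to 20, r = 0.5), with baseline truncated at language-specific thresholds, gave variance ratios of 1.016 to 1.048. The mean error in the treatment effect was at most about 0.03 CAT-MH points, with or without the language term.

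**The case against.** The strongest reply is that adjusting for baseline and site is a valid, standard choice, that the gain is small, and that its size rests on undocumented inputs. All of that stands, and it is why this is an optional improvement and not an error. Three stronger readings are tempting, and the documents do not support them.

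- **That enrolled participants' scores run 8 to 10 points lower in Spanish or Chinese.** A reader might infer this from the cut-offs. They are thresholds only: the plan gives no reason for them and no means or SDs by language. Because entry is possible on either scale or through the Major Depressive Disorder result, an enrolled participant's score on a given scale may lie below its own cut-off.
- **That the treatment comparison is biased.** Randomisation protects it, and the simulation agrees.
- **That imputed CAT-MH scores will be wrong by language.** If dropout is related to language, the open-ended auxiliary clause already calls for language in the imputation model; age and gender are only examples. The language-subgroup imputation includes it regardless. What remains is that the main imputation models do not name it in advance, so a likely predictor of the outcome enters only if it is also associated with missingness.

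A related worry is that the exploratory baseline-severity subgroups would sort partly by language if one CAT-MH cut-off defined them. The plan does not say which measure defines severity, so this cannot be held against it.

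It can also be said that any prognostic variable could be proposed on the same logic. Language differs in that the plan itself treats the CAT-MH scale as language-dependent when deciding who enters.

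**Conclusion.** The point holds as a minor matter of precision. The plan uses language-specific CAT-MH thresholds at entry but no language term in the main models for its four key secondary CAT-MH tests.

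If the threshold gap carries over as a constant offset at baseline and follow-up, omitting language leaves about 0.6% to 7.4% of the remaining variance unexplained that could be explained. The typical figure is 2% to 3%, equivalent to roughly 20 to 35 of 1,044 participants or about one point of power. The offset, the SD, the correlation and the language split are all assumptions. A smaller offset among enrolled participants would make the gain smaller. No conclusion about the treatment effect is put in doubt.

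**What to change.** In VII.A, Statistical Analyses, add language of CAT-MH administration (English versus Spanish/Chinese, matching the grouping of the cut-offs) as a fixed covariate in the CAT-MH depression and CAT-MH anxiety models at months 6 and 12. In VII.B, name the same variable as a predictor in the CAT-MH imputation models, so that imputation and analysis models agree and its inclusion does not wait on a test of missingness.

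The cost is one degree of freedom per model and a short SAP edit. No new data are needed, since the entry cut-offs can be applied only if the language of administration is known, and no participants are lost. The change should be made before unblinded outcome data are examined.
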